## 1. Introduction

The goal of this interventional study was to examine the efficacy of the online mindfulness-based cognitive therapy program(MBCT) in youth (18-25 years old) with depressive symptoms. The main questions it aimed to answer were: Whether the program could reduce depressive symptoms in university students. Whether the program could increase the quality of life in university students. The effectiveness, acceptance, and practicability of the program for university students. Participants in the experimental group would be arranged to attend online mindfulness-based cognitive programs for eight weeks. The control group would be educated with the knowledge of mental health to manage their negative emotions.

## 2. Statistical Analysis Plan (SAP)

A randomized controlled trial (RCT) was conducted to examine the efficacy of the online mindfulness-based cognitive therapy program(MBCT) in youth (18-25 years old) with depressive symptoms. The investigators expected the online MBCT program could assist university students in reducing their depressive mood and facilitating quality of life. The investigators also discussed the effectiveness, acceptance, and practicability of the online MBCT program to the subjects.

### 2.1 Study design

Participants in the experimental group would be arranged to attend online mindfulness-based cognitive programs for eight weeks. Each week was divided into 3 parts: detailed skill training with pictures or short videos, techniques application in different scenarios, and concepts consolidation through a web-based assignment.

Participants were requested to complete the 3 parts above, which would take approximately 15 minutes in total per week. The content of the online intervention includes 8 chapters reflecting multiple topics (e.g. explaining MBCT, automatic pilot, awareness of mood, accentedness, staying with the present experience, linking habitual reactions to the unpleasant event, using breathing and body as an anchor, and planning to continue mindfulness practice) which were delivered to subjects each week by the research team.

Participants in the control group would acquire knowledge of mental health to manage their negative emotions. There would be 2 times of mental health education and one web-based assignment including writing feedback to ensure learning effectiveness each week. The content for 8 weeks would include knowledge about depression, recognition of depression and depressive mood, symptom management, adaptation skills and coping skills, myths of depression, depression prevention, and referral information for mental health. The investigators would evaluate the effectiveness of the two groups using the outcome assessment of BDI-II, WHOQOL-BREF, BAI, OSA, and COPM 1 week before intervention (pre-test) and 1 week after intervention (post-test).

### 2.2 Populations and subgroups to be analysed

This study would use a Survey Cake form, announced through the university website or online platforms, to recruit participants, primarily targeting undergraduate students at a certain medical university in Taichung, Taiwan. Participants would be screened through the BDI-II and the basic information questionnaire. The inclusion criteria were as follows: (1) aged between 18 and 25 years; (2) scoring at least mild on the Beck Depression Inventory-II (BDI-II); (3) having the LINE messaging application; and (4) being literate and willing to participate in the study. Exclusion criteria were: (1) self-reported other mental illnesses such as schizophrenia or bipolar disorder; (2)

self-reported major physical illnesses such as cancer or stroke; and (3) unwillingness to accept random assignment. The sample size was estimated that a correlational study requires at least 30 participants. Considering potential dropouts or inability to complete the online study, a 35% attrition rate was applied, resulting in a minimum of 46 valid questionnaires being collected. Participants would then be randomly assigned, with 23 in the experimental group and 23 in the control group.

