### 2.4 Analyses

The study would use descriptive statistics to record and analyze the basic information and follow-up measurement data of the participants, described in terms of percentages, means, and standard deviations. Changes in depression levels and quality of life between the experimental and control groups would be analyzed using a mixed-effects model to verify the effectiveness of the "Online Mindfulness Cognitive Skills" program on depression and quality of life among students with depressive tendencies. The analysis would be conducted using SAS 9.4 statistical software, with a significance level set at  $\alpha = 0.05$ .

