#### **Approved Research Design**

The research design has been reviewed and approved by the National Science Council (NSC). The study's feasibility and structure are appropriate for the research objectives. This study utilizes a "randomized controlled trial" design, where the experimental group will receive an eight-week "Online Mindfulness Cognitive Skills" program, delivered once a week via the LINE social platform, while the control group will be provided with information on depression and self-emotion management. To ensure the well-being of participants, the co-investigator will monitor and engage with participants weekly through messages on the online platform. The informed consent form clearly states that researchers will send information to participants via a social platform on mobile devices each week and invite them to complete questionnaires. Participants can freely choose the time and place to review the information and complete the questionnaires. The procedures and methods of this study are integrated into daily life activities.

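### The sample size rests on a rule for a correlational study, which does not support it for the between-arm comparison the trial plans

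*Combined protocol and SAP*

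**What the plan says.** Section 2.2 contains the only sample-size reasoning in the documents: "The sample size was estimated that a correlational study requires at least 30 participants". It continues: "a 35% attrition rate was applied, resulting in a minimum of 46 valid questionnaires being collected". The result is split equally: "Participants would then be randomly assigned, with 23 in the experimental group and 23 in the control group".

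Section 2 and the part headed Approved Research Design both describe a randomised controlled trial of efficacy. Section 2.4 states the analysis: "Changes in depression levels and quality of life between the experimental and control groups would be analyzed using a mixed-effects model", at a significance level of 0.05, with the aim of verifying that the program works. Section 2.1 has both arms assessed at two visits, "using the outcome assessment of BDI-II, WHOQOL-BREF, BAI, OSA, and COPM 1 week before intervention (pre-test) and 1 week after intervention (post-test".

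No correlation analysis is planned anywhere. Nor do the documents give a target between-arm difference, an SD, a pre-post correlation or a power, and nothing suggests that such a figure was redacted.

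**The concern.** A sample-size rule supports a design only for the analysis it was made for. A minimum of 30 for a correlational study is a whole-sample total for estimating an association in one group. The planned contrast is a difference between two randomised groups, and its precision depends on the number per arm, the outcome SD and the pre-post correlation. The stated rule uses none of these.

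What is lost is prior information. Someone reading 2.2 cannot know what difference in depression or quality of life the trial was expected to detect, and could take the rule as assurance about the efficacy comparison that it does not provide. This matters most if the result is non-significant. Without a statement of expected precision, such a result is easily read as absence of effect.

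**Working it through.** **1. The plan's own figure.** 30 / (1 − 0.35) = 46.15, stated as 46 (47 if rounded up). The inflation step reproduces to within rounding. The starting value of 30 cannot be reproduced, because no effect, SD or power lies behind it.

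**2. Inputs.** From the documents: 23 per arm, 35% attrition, two visits, alpha 0.05. Assumed, because the documents do not say: two-sided test, 80% power, equal SDs between arms, equal loss per arm, and pre-post correlation ρ of 0.3, 0.5 or 0.7. Differences are in post-test SD units.

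Completers per arm: 46 × 0.65 / 2 = 14.95, so 15 if 46 is the number enrolled and the stated loss occurs; 23 if nobody is lost.

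**3. Unadjusted post-test comparison.** SE = √(2/n), which is 0.365 at n = 15 and 0.295 at n = 23. By the noncentral t (28 and 44 df), the detectable difference is 1.06 SD and 0.84 SD. The 95% CI half-width is 0.75 and 0.59 SD.

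**4. Baseline-adjusted or baseline-constrained model.** Multiply the SE by √(1 − ρ²). At ρ = 0.5 and n = 15: 0.365 × 0.866 = 0.316, and 1.060 × 0.866 = 0.918. Generalised least squares with 23 pre-test and 15 post-test values per arm and a common baseline mean gives the same result, and it does not depend on the baseline SD. Taking off one degree of freedom and allowing for chance baseline imbalance raises the figures only slightly (at n = 15: 1.03 / 0.94 / 0.77).

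**5. Unconstrained group-by-time test,** equal SD at both visits, dropouts' baselines kept. SE² = 2 × [(1 − ρ²)/n_post + (1 − ρ)²/23]. At ρ = 0.5 and n_post = 15: 2 × (0.75/15 + 0.25/23) = 0.1217, so SE = 0.349. The detectable difference is 0.349 × (1.060/0.365) ≈ 1.01 SD. With 23 at both visits the SE becomes √(4(1 − ρ)/23).

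| Model | Completers per arm | Detectable difference, SD (ρ = 0.3 / 0.5 / 0.7) | 95% CI half-width, SD |
|---|---|---|---|
| Baseline-adjusted or constrained | 15 | 1.01 / 0.92 / 0.76 | 0.71 / 0.65 / 0.53 |
| Baseline-adjusted or constrained | 23 | 0.81 / 0.73 / 0.60 | 0.57 / 0.51 / 0.42 |
| Unconstrained group-by-time | 15 | 1.18 / 1.01 / 0.80 | 0.83 / 0.71 / 0.56 |
| Unconstrained group-by-time | 23 | 1.00 / 0.84 / 0.65 | 0.70 / 0.59 / 0.46 |

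If the group-by-time analysis used completers only, the figures at 15 per arm would be 1.25 / 1.06 / 0.82 SD.

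**6. Does this show that 46 is too few?** Power of the baseline-adjusted model, for two assumed true effects:

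| Assumed effect | 15 per arm (ρ = 0.3 to 0.7) | 23 per arm (ρ = 0.3 to 0.7) |
|---|---|---|
| 0.5 SD | 28% to 46% | 41% to 64% |
| 0.8 SD | 60% to 84% | 79% to 96% |

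The answer turns on a target effect that the documents never name.

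**The case against.** The sponsor can fairly say that a small trial of a low-risk online program need not be sized by a power calculation, that the attrition step is sound, and that the model in 2.4 is valid whatever rule set the number. Most of this stands. No estimate, test or error rate in 2.4 becomes wrong because of 2.2. But the documents never call the trial a pilot, and 2.4 sets out to verify effectiveness at 0.05. A rule for another kind of study is not a justification for that, even where none is strictly required.

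Two stronger readings are tempting, and the documents support neither. The first is that 46 is too small. The power and correlation figures above are assumptions, and with a large effect and a strong correlation 46 could be enough. The second is that a non-significant result could not be interpreted. The planned model will give an estimate and a confidence interval, and the interval shows which differences the data rule out. What is missing is the statement in advance.

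A further objection is that the more favourable figures come from a baseline-adjusted model that 2.4 does not name, since its wording on changes between groups reads most naturally as a group-by-time test. That is right, which is why both sets are given.

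**Conclusion.** The point holds: the stated rule is for a different kind of study and does not support the size for the planned comparison, and 2.2 does not say what the design can detect. It is a fault of justification that should be corrected; it does not invalidate the trial.

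Across the two models and 15 to 23 completers per arm, the detectable difference runs from about 0.60 to 1.18 SD, all under the assumptions listed in the working. For depression, entry requires "scoring at least mild on the Beck Depression Inventory-II (BDI-II", which may reduce both the baseline SD and the correlation. A lower correlation moves the baseline-constrained figures toward 1.01 SD (15 per arm) or 0.81 SD (23 per arm). The unconstrained figures also depend on the baseline SD.

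The depression figures carry one more condition. The Self-Assessment Questionnaire part of 2.3 says the BDI-II serves for screening alone, while 2.1 lists it as an outcome at both visits. Until those two statements are reconciled, the depression figures have no settled instrument. The point holds for quality of life either way.

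**What to change.** **In 2.2:** keep the 30-to-46 sentence only as a record of how the number was chosen, and add wording such as:

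> The number was not derived from a power calculation for the between-arm comparison. For each efficacy outcome, assuming two-sided 0.05, 80% power, equal SDs between arms and a pre-post correlation of 0.3 to 0.7, the baseline-constrained model can detect about 0.76 to 1.01 SD with 15 completers per arm (95% CI half-width 0.53 to 0.71) and 0.60 to 0.81 SD with 23 per arm (0.42 to 0.57). A non-significant result will be reported with its confidence interval and will not be read as absence of effect.

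If an unconstrained group-by-time test is kept, quote instead 0.80 to 1.18 SD with 15 completers per arm and dropouts' baselines included (half-width 0.56 to 0.83), and 0.65 to 1.00 SD with 23 (0.46 to 0.70), stating that equal SDs at both visits are assumed.

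**In 2.4 (optional, separable from the correction to 2.2):** specify that the mixed model constrains or adjusts for the pre-test value, which is already collected. This narrows the interval at no cost in data. Section 2 speaks of the trial as already conducted, although the tense is mixed elsewhere. If outcome data have been seen, date and disclose the choice, and also report the model planned before the data were seen.

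**In 2.1 and 2.3:** reconcile the role of the BDI-II before quoting any depression figure.

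**Cost:** wording only, plus the disclosure just described if it applies. No added enrolment and no change to the attrition figure. The downside is that the stated justification becomes less favourable and depends on an assumed correlation.

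### Allocation of 46 students does not use the screening BDI-II score; stratifying on it would be a cheap, minor gain, mostly if the change analysis is not baseline-adjusted

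*Combined protocol and SAP*

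**What the plan says.** Section 2.2 is the only place that describes allocation: "Participants would then be randomly assigned, with 23 in the experimental group and 23 in the control group". Neither the protocol text nor the SAP text mentions stratification, blocking, minimisation or how the sequence is generated.

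The same section says "Participants would be screened through the BDI-II and the basic information questionnaire", and one entry criterion is "scoring at least mild on the Beck Depression Inventory-II (BDI-II"), with no upper limit. Assignment is described after the collection of at least 46 questionnaires, so the natural reading is that every BDI-II score is in hand before anyone is allocated.

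Section 2.4 gives the analysis: "Changes in depression levels and quality of life between the experimental and control groups would be analyzed using a mixed-effects model". It lists no fixed effects, no baseline covariate and no common baseline mean for the two arms.

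The documents disagree on the role of BDI-II. Section 2.1 lists it among the outcomes measured before and after the intervention. The self-assessment text in section 2.3 restricts it to screening.

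**The concern.** In a trial this small, chance alone can leave one arm noticeably more depressed at the start. The score that would prevent most of this is already collected and goes unused at allocation. If section 2.4 is then carried out as a plain comparison of changes, the arm that started worse will tend to fall further through regression to the mean. A positive result in such a trial would be open to doubt. As written, the plan commits to no protection at either stage: no balancing at allocation and no stated baseline term in the model. Balancing on severity could also help the quality-of-life comparison and even out drop-out, as far as either is related to severity. The documents do not say whether they are.

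**Working it through.** **The plan's own figure.** Section 2.2 starts from 30 and applies 35% attrition: 30/(1 - 0.35) = 46.15. The stated 46 is reproduced to within rounding (47 if rounded up), and 46/2 = 23 per arm. No effect size, SD or power is given.

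**Inputs.** From the documents: 23 per arm, BDI-II measured at screening, a mixed model of change, 35% attrition. Assumed: a normal baseline score unless stated otherwise, equal pre and post SDs, pre/post correlation r of 0.3 to 0.7, and a screening score that is also the pre-test. Differences are in baseline SD units because no BDI-II SD is given.

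**1. Chance imbalance without stratification.** SE of the baseline difference = sqrt(2/23) = 0.295.
- 0.3/0.295 = 1.02, two-sided tail 31%.
- 0.5/0.295 = 1.70, two-sided tail 9%.

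If 35% are lost regardless of severity, 46 × 0.65 = 29.9 remain, about 15 per arm. The SE becomes sqrt(2/15) = 0.365 and the chances 41% and 17%.

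**2. With a median split.** In 20,000 simulated allocations the SD of the baseline difference fell from 0.296 to 0.192 (normal score), or to 0.214 for a skewed score truncated at an assumed entry cut-off. The normal figure can be checked by hand for a 12/11 and 11/12 split:
- The SD within each half of a normal distribution is sqrt(1 - 2/π) = 0.603, which gives 0.603 × 0.295 = 0.178.
- The unequal split adds an offset of (1/23) × 2 × sqrt(2/π) = 0.069.
- Together, sqrt(0.178² + 0.069²) = 0.191.

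Then 0.3/0.192 = 1.56 gives about 12%, and 0.5/0.192 = 2.60 gives about 1%. For the skewed score the simulated chance of 0.3 SD or more was 17%. A separate simulation with blocks of four in two strata gave about 10% and 0.6%.

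**3. Effect of a gap on an unadjusted change contrast.** The post-test follows the pre-test with slope r, so a gap D moves the contrast by rD - D = -(1-r)D.

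| r | D = 0.3 SD | D = 0.5 SD |
|---|---|---|
| 0.3 | 0.21 | 0.35 |
| 0.5 | 0.15 | 0.25 |
| 0.7 | 0.09 | 0.15 |

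The shift favours the arm that started worse. Simulated slopes without stratification were -0.69, -0.51 and -0.31. With the pre-test as covariate they lay between -0.009 and 0.009. Over all randomisations the mean error of the unadjusted contrast was -0.002 to 0.008 SD and its type I error 4.9% to 5.2%.

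**4. Variance of the unadjusted contrast.** It is proportional to (1 - r²) + (1 - r)²k. Here k = 1 without stratification, (0.192/0.296)² = 0.42 for the normal score and (0.214/0.296)² = 0.52 for the skewed score.

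| r | k = 1 | k = 0.42 | k = 0.52 |
|---|---|---|---|
| 0.3 | 1.40 | 1.12 (20% lower) | 1.16 (17% lower) |
| 0.5 | 1.00 | 0.86 (14% lower) | 0.88 (12% lower) |
| 0.7 | 0.60 | 0.55 (9% lower) | 0.56 (7% lower) |

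**5. With baseline adjustment.** Chance imbalance inflates the variance of the adjusted estimate by 2.4% on average without stratification and by 1.0% to 1.2% with it. The added gain is therefore about 1%.

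**6. Which model term is needed.** After two-stratum allocation, a change test that ignores the stratum rejected in 2.7%, 3.4% and 3.7% of null trials at r = 0.3, 0.5 and 0.7 (a second simulation gave 2.8%, 3.4% and 4.2%), so it is conservative. A stratum main effect cancels out of each student's pre-to-post difference. In three simulated complete datasets it left the group-by-time estimate identical and its SE the same to within 0.0001. A stratum-by-time term, or the stratum as a covariate on the change score, restored about 5%.

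**The case against.** A reader might infer that the planned comparison of changes is biased. The documents do not support that. Simple 23/23 randomisation is valid, its average error is zero, and its p-value already allows for chance imbalance. A shift exists only within a trial that turns out imbalanced, and only if baseline is left out of the model. Section 2.4 does not say whether it is. This objection stands.

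It can also be said that the real gap is the unspecified model, because baseline adjustment delivers nearly all of the protection. That stands too, and it is why the allocation point is minor. It does not remove the point, since the plan does not commit to adjustment.

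Several premises are assumptions. The documents give no BDI-II distribution, no pre/post correlation and no link between severity and drop-out. If screening and the pre-test one week before the intervention are separate measurements, balance on the pre-test would be weaker than calculated.

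Finally, section 2 speaks of the trial as already conducted, though the tense varies. If allocation is complete, only the change to the analysis remains open.

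**Conclusion.** The point holds as a minor design weakness. The screening score is available and unused, and with 23 per arm a severity gap of 0.3 SD or more has a chance of about 31%, against about 12% with a median split (0.5 SD or more: about 9% against 1%). What this costs depends on section 2.4. Without baseline adjustment, stratification would lower the variance of the change contrast by about 7-20% over r = 0.7 to 0.3 and the two score shapes examined. With adjustment, the extra benefit is about 1%. These figures rest on the stated assumptions, chiefly that the screening score also serves as the pre-test. The absence of stratification is not an error and does not by itself invalidate a result.

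The conflict over BDI-II affects the size of the benefit, because it decides whether a BDI-II change is analysed at all. On either reading the score exists before allocation and could be used.

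**What to change.** **Section 2.2.** State that, once the cohort of 46 is assembled, allocation is stratified at the median screening BDI-II. Use a computer-generated list fixed at 12/11 in one stratum and 11/12 in the other, so that each arm has 23, and draw at random which arm takes the 12 in the lower stratum. Small blocks alone would not do this: each stratum holds 23, an odd number, so incomplete blocks cannot guarantee 23 per arm. If students are instead allocated as they enrol, the median is not yet known and a cut set in advance would be needed. The gains above were not calculated for such a cut.

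**Section 2.4.** Write out the model and let baseline severity act on the change, either through baseline BDI-II as a covariate or through a stratum-by-time term. A stratum main effect alone is not enough. This part is worth making even if allocation has already taken place.

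**Sections 2.1 and 2.3.** Reconcile whether BDI-II is a pre/post outcome or is used for screening only.

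**Cost.** A few sentences, a stratified list in place of a simple one, and about one degree of freedom. No extra participants or data are needed.

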### 2.3 Outcomes

#### Baseline Characteristics

The contents included the subject's gender, age, grade, living situation, employment status, economic status, whether there was a diagnosis of mental or physical illness (if so, the subject was asked to provide the name of the diagnosing hospital and physician), whether there was any psychological treatment involving medication (if so, the subject was asked to provide the frequency and location of treatment), contact phone number, and LINE ID.

